10.2 Monitoring for Efficacy and Toxicity

(Data Safety Monitoring Committee [DSMC])

The principal investigators (Drs. [name] and [name]), the Lead research nurse ([name]), and the statistician ([name]) will make up the Data Safety and Monitoring Committee for this trial. This is a Level 1 trial and will be monitored by The Johns Hopkins Clinical Research Office. The function and role of the Data Safety Monitoring Committee will review the protocol per their institutional standards to help ensure that the trial is running safely.

10.3 Analysis of Endpoints

10.3.1. To achieve a prevalence of grade 3+ toxicities between six months and two years post-treatment <15% while maintaining a locoregional tumor control of at least 85% during the same time interval.

The primary endpoints, prevalence of toxicity and locoregional control rate, will be reported for all patients with an exact 95% confidence interval.

10.3.2. To determine the nature and prevalence of side effects at different time intervals and describe their relationship to pre-treatment function (toxicity) and local dose and treated volume.

Patients will be grouped by whether they had none or a grade 0-2 toxicity versus a grade 3+ toxicity. We will tabulate the frequency of patients in each group by a dichotomous measure of dose and tests for differences with a Chi-square or Fisher's exact test. Patients will also be grouped dichotomously by the number of side effects experienced

and frequencies will be compared to dose category and toxicity category using Chi-square or Fisher's exact tests.

10.3.3. To determine the quality of life of surviving patients.

The results of the Head and Neck MD Anderson Symptom Inventory (MDASI-HN) will be calculated for each patient. The mean score will be reported with a 95% confidence interval. The range and quartiles of the distribution of scores will also be reported.

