2 OBJECTIVES

2.1 To achieve a prevalence of grade 3+ late toxicity at 2 yrs <15% while maintaining a locoregional tumor control >85±7% at the same time interval (toxicity is scored at 5.11 and 9.5 and locoregional control at 9.4);

2.2 To determine the nature and prevalence of side effects at different time intervals and describe their relationship to pretreatment function and local dose and treated volume.

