4 PRETREATMENT EVALUATIONS

- 4.1 Each patient must have completed the following studies prior to irradiation:
 - 4.1.1 Complete history and physical exam including weight and performance status.

4.1.2 Complete dental evaluation. Any required dental extractions must be made and fluoride prophylaxis instituted prior to radiotherapy.

4.1.3 Speech pathology evaluation including instrumental swallowing assessment or clinical assessment of swallowing and administration of pretreatment swallowing and trismus exercises (*This assessment is a standard of care assessment for this patient population). Completion of pretreatment MD Anderson Dysphagia Inventory (MDADI) and Montreal Cognitive Assessment (MCA). Speech therapy evaluation has to take place before commencement of treatment.

4.1.4 Nutritional evaluation to be conducted within the first week of starting (chemo)radiation therapy.

4.1.5 Completion of the following laboratory studies: CBC with diff. and platelets, Metabolic Panel to include- sodium, potassium, glucose, calcium, magnesium, BUN, serum creatinine, total protein, albumin, alkaline phosphatase, total bilirubin, AST, ALT, and a creatinine clearance)

4.1.6 Completion of the following radiologic studies: CT of head and neck with < 3 mm contiguous slices in immobilization system (*with contrast, unless contraindicated*); whole body PET/CT (integration of both high resolution CT with contrast and dedicated PET acquisition through the head and neck are strongly suggested); MRI of head and neck with gadolinium including T1 and T2 weighted sequences in at least 2 different planes strongly suggested for primary tumors of the base of tongue (*optional-see 5.1.2*).

4.1.7 Audiogram to be conducted before or within the first week of starting therapy (*if inner ear is to be irradiated at mean dose ≥ 40 Gy*).

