5.4 Organ At Risk (OAR) Definitions

Several organs at risk will be contoured on each patient planning CT as follows. In order to facilitate the spelling, a script will be run from Pinnacle to generate the regions of interest. OAR's are: mandible, brain, brainstem, cord, submandibular glands, thyroid gland, parotid glands, upper gastrointestinal mucosa⁴⁷, larynx⁴⁵, masticatory spaces, upper, middle and inferior constrictor muscles, cricopharyngeous muscle, esophagus, brachial plexuses, temporomandibular joints (TMJ), inner ears, internal, external and common carotid arteries. Paired organs will be divided into those on the dominant side of disease (dominant) and those on the opposite side (contralateral). An atlas on how to contour each structure is available at the web site of the University of Texas Medical Branch, <http://www.utmb.edu/radoncology/oar.htm> For planning purposes, the cord is expanded by 4 mm.

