5.10 Quality Assurance of Target Volumes and Critical Structure Volumes

The DVH's of each target and Oar will be exported and converted to excel file format.

5.10.1 Each treatment shall be scored with regard to the coverage of each PTV (*i.e.* *PTV70*, *PTV63*, *PTV58.1*, and *PTV50.75*) and with regard to the level of sparing of several OAR's; the scores to be assigned are defined in table 8 below.

Table 8.

	Per protocol	Minor variation	Major variation
Overall treatment time	47 days	48-51 days	>51 days
PTV coverage	V95%>99%	95%<V95%<99%	V95%<95%
Cord + 4 mm	Max Dose 45Gy	Max Dose 47.5Gy	Max Dose 49.5Gy
Brainstem	Max Dose 54Gy	Max Dose 56.7Gy	Max Dose ≤ 59.4Gy
Brain	Max Dose 60Gy	Max Dose 63Gy	Max Dose 66Gy
Larynx for edema	V50 < 30%	30% < V50 < 31.5%	31.5% < V50 < 33%
Mandible	Max Dose 70Gy	Max Dose 73.5Gy	Max Dose 75Gy
Superior constrictor	V40 < 95%	95% < V40 < 100%	
Superior constrictor	V50 < 90%	90% < V50 < 94.5%	94.5% V50 < 99%
Superior constrictor	V60 < 80%	80% < V60 < 84%	84% < V60 < 88%
Superior constrictor	V65 < 70%	70% < V65 < 73.5%	73.5% < V65 < 77%
Parotids	V30 < 50%	50% < V30 < 52.5%	52.5% < V30 < 55%
Esophagus	Max Dose 45Gy	Max Dose 47.3Gy	Max Dose 49.5Gy
Brachial plexus	Max Dose 60Gy	Max Dose 63Gy	Max Dose 66Gy
Inner Ears	Mean Dose 40Gy	Mean Dose 42.5Gy	Mean Dose 45Gy

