9 PATIENT ASSESSMENTS

9.1 Patient Assessments

Table 9.

	Pretreatment	During treatment ¹	Follow up ²
Weight & PS	X	X	X
History & Physical	X		
Dental Evaluation	X		
Nutritional evaluation	X ³	X ³	
CBC with diff. and platelet count	X	X ¹⁵	
CMP ¹⁸	X	X ¹⁵	
Creatinine Clearance	X	X ¹⁷	
Pregnancy Test	X ¹⁶		
Thyroid Function Test (TSH)	X		X
PET/CT (CT w contrast)	X		X ⁵
MRI of head and neck	X ⁶		X ⁵
Toxicity Evaluation ⁷	X	X	X
Flexible fibroscope ¹⁰	X		X
Audiogram ¹⁴	X	X	X
Speech therapy evaluation ¹²	X	X ⁸	X ⁹
MBSS			X ¹¹
Biopsy	X ¹³		X ¹³
Appendix 2 & 3	X	X	X

1. Weekly during radiotherapy

2. Follow-up will be performed 6-8 weeks after the end of RT (+ or – 7 days), at 3 months (+ or - 14 days) after the end of radiotherapy and every 3 months thereafter for the first two years; then every 6 months (+ or – 30 days) during years 3 to 5

3. Initial evaluation must be done within a week of starting therapy and then as clinically indicated. On treatment nutrition evaluations will be performed as clinically indicated.

4. Every 6 months for 5 years

5. PET/CT is required at 10-12 weeks after the end of treatment to evaluate response. Afterwards a PET/CT should be obtained at the discretion of treating physician. Alternatively a CT or MRI can be obtained if a PET/CT is not approved.

6. A pre-study MRI is at the discretion of the treating physician

7. See 5.12

8. At approximately the 4th week of treatment

9. To be performed 6-8 weeks, 6 months, and 12 months after the end of RT

10. Primary tumor assessment may require the use of a flexible fibroscope as deemed by the treating physician.

11. To be performed at 6-8 weeks and 12 months even in absence of specific symptoms

12. The MD Anderson Dysphagia Inventory (MDADI) will be given at each visit; the Montreal Cognitive Assessment (MCA) will only be given at baseline and 6-8 weeks after completion

13. Pretreatment Biopsy can be done outside JH provided that pathology blocks are submitted at JH for review and HPV testing; During follow up, any suspicious mucosal lesion in the upper aerodigestive tract should trigger a search for recurrent disease that may or may not include a biopsy; in the latter case, the biopsy can be done at JH or outside, but, again, the pathology specimen must be reviewed at JH. No further HPV testing is necessary on the repeat biopsy.

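### Section 10.3.2 tests dose only as an undefined two-level variable, states no analysis of treated volume and does not clearly use baseline toxicity, although objective 2.2 asks for all three

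*Combined protocol and SAP*

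**What the plan says.** Objective 2.2 undertakes to determine the nature and prevalence of side effects and to "describe their relationship to pretreatment function and local dose and treated volume". The heading of section 10.3.2 repeats this with one gloss: "describe their relationship to pre-treatment function (toxicity) and local dose and treated volume".

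The analysis text under that heading has two parts. First, patients are grouped as grade 0-2 (or none) against grade 3+, and "We will tabulate the frequency of patients in each group by a dichotomous measure of dose", with a Chi-square or Fisher's exact test. Second, the number of side effects is dichotomised and "frequencies will be compared to dose category and toxicity category using Chi-square or Fisher's exact tests".

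The data for a fuller analysis are already collected:
- Section 5.10: "The DVH's of each target and Oar will be exported and converted to excel file format".
- Section 5.4 lists 21 structures to contour, before paired organs are divided by side.
- Table 9 schedules a toxicity evaluation before treatment, which section 5.12.1 scores by CTCAE 4.0. Its notes add: "The MD Anderson Dysphagia Inventory (MDADI) will be given at each visit".

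**The concern.** The objective names three explanatory factors, and the analysis text clearly handles one of them, in its coarsest form. Followed as written, the plan produces no stated result for treated volume and leaves the use of baseline status to interpretation.

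For dose, the two-level variable is not defined. Section 5.6 gives four dose levels within a single treatment plan, so prescription offers no natural division of patients into two groups by local dose. The choice of organ, metric, cut-point and interval is left to the analysis stage. This has two costs: information is lost if the true relationship is graded, and the nominal error rate no longer holds if the split is chosen after looking at the results.

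**Working it through.** **The plan's own figures.** Section 10.3.2 states no sample size, power or alpha. The figures behind it, in section 10.1, reproduce: 60 × (1 − 0.15) = 51 against the stated 50; the exact 95% interval for 7/50 is 5.8-26.7% (stated 6-27%), and for 42/50 it is 70.9-92.8% (stated 71-93%).

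**Objective against analysis.**
- Local dose: a two-level variable; organ, metric, cut-point and interval not stated.
- Treated volume: in the heading, but in no stated analysis. A Vx criterion could carry volume, but the text does not say that one is meant.
- Pretreatment function: glossed in the heading as toxicity, most naturally the baseline CTCAE grade. The analysis text defines its groups only as grade 0-2 against 3+, with no pretreatment time point, so no test clearly uses a baseline value.

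**Inputs for the size.** n = 50 (section 10.1). Event rates: 15% (the section 10.1 target), or 50 × 0.15 = 7.5 events; and 30.9% (the 2-year figure from the prospective study in section 1.4), or 50 × 0.309 = 15.5 events. The documents give no dose-response shape or effect size. I assume one normally distributed dose metric and a logistic outcome, with a range of odds ratios per SD. Two-sided 5%; 6,000 simulated trials per setting, so the Monte Carlo standard error is at most √(0.25/6000) = 0.65 points.

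**Smooth effect, fixed median split (power).**

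| Events | OR per SD | Fisher | Chi-square | Rank test |
|---|---|---|---|---|
| 15% | 1.5 | 5.6% | 12.7% | 15.1% |
| 15% | 2 | 13.5% | 25.6% | 34.3% |
| 15% | 2.5 | 23.0% | 38.4% | 51.0% |
| 15% | 3 | 31.7% | 48.5% | 63.9% |
| 31% | 1.5 | 10.7% | 18.3% | 23.6% |
| 31% | 2 | 26.8% | 39.3% | 51.2% |
| 31% | 2.5 | 42.9% | 57.4% | 72.7% |
| 31% | 3 | 57.9% | 70.4% | 86.0% |

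For OR 2 to 3, rank minus Chi-square runs from 34.3 − 25.6 = 8.7 to 86.0 − 70.4 = 15.6 points. Rank minus Fisher runs from 34.3 − 13.5 = 20.8 to 63.9 − 31.7 = 32.2 points. At OR 1.5 the gain over Chi-square is 2-5 points. With about 3 events (6%, OR 2.5) there is no gain: rank 27%, Chi-square on a top-30% split 31%.

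**No effect, false-positive rate.**
- Fixed median split: Fisher 2%, Chi-square 5%.
- Best of the 30/50/70% splits: Fisher 6.5% and 7.4%, Chi-square 12.9% and 11.5% (15% and 31% events).
- Best of every split from 20% to 80%: Fisher 18.6% and 21.2%, Chi-square 27.2% and 28.8%.

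**True threshold (5,000 runs, four scenarios).** With the cut exactly on the threshold, Chi-square beats the rank test by 13-19 points; for example, with 5% against 25% at the median, 54% against 39%. With a misplaced cut, Chi-square falls 10-52 points below the rank test.

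**Precision (about 500 runs).** At OR 2.5, one-covariate Firth regression gives a median 95% interval of 0.99-6.54 at 15% events and 1.21-5.56 at 31%.

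**The case against.** The best reply is that the objective only undertakes to describe, claims no power or alpha, and rests on so few late events that any method is imprecise. That stands, and it limits the weight of the point. Much of the shortfall against Fisher is also Fisher's own conservatism: at 15% events and OR 2.5, 38.4 − 23.0 = 15 of the 28 points.

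Four stronger readings are tempting, and the documents do not support them:
- **A reader might infer that the plan has no baseline measure at all.** The heading points to toxicity, and Table 9 schedules it before treatment. What is missing is a test that clearly uses it.
- **A reader might infer that the protocol offers no dose-volume threshold.** Section 1.5 gives oral-mucosa cut-offs linked to PEG need (V9.5 below 64.5 cc and V10 below 54 cc, in Gy per week). The first reappears in Table 7 as V66.5 Gy, since 9.5 × 7 = 66.5. Table 8 gives organ limits such as parotid V30 and larynx V50. The fault is that 10.3.2 refers to none of them. Because this background is threshold-based, the scenario in which a well-placed split wins deserves real weight.
- **A reader might take 19-29% as the error rate of the planned test.** It is the worst case of a full search, which the plan does not prescribe. It also applies only when there is no true effect.
- **A reader might infer that continuous metrics solve multiplicity.** They do not. Two metrics in each of two intervals give at least one nominally significant result in 14-17% of null trials, and three metrics in 18-24% (assuming 15% and 40% events). The remedy needs its own limit on tests.

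**Conclusion.** The point holds as a low-cost improvement. Section 10.3.2 leaves the volume part of objective 2.2 without a stated analysis, leaves the baseline part ambiguous, and leaves the dose variable open to choice after the data.

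Under a smooth dose-response with OR 2 to 3 per SD, the median split costs 9-16 points of power by Chi-square and 21-32 by Fisher. The gain over Chi-square is negligible at OR 1.5 or about 3 events, and the ordering reverses if a true threshold lies exactly at the cut. A post-hoc choice of cut raises the null error to about 7-13% with three candidate splits and 19-29% at worst. All of these sizes rest on assumed effects and a normally distributed metric. The gap in the text does not depend on them.

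The primary endpoints, their confidence intervals and the tabulation of side-effect prevalence are unaffected.

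**What to change.** In section 10.3.2:
- Replace the dichotomous dose measure with one prespecified continuous organ-dose metric and one prespecified volume metric (a Vx or the treated PTV volume), both from the exported DVHs.
- Compare each between grade 0-2 and grade 3+ of a toxicity relevant to that organ, in a stated interval, by rank-sum test or one-covariate Firth logistic regression. Report estimates with 95% confidence intervals.
- Tabulate toxicity by the baseline CTCAE grade of the same toxicity.
- If a split is kept as a supplement, take its cut-off from the protocol (for example the mucosa volume in section 1.5 and Table 7, or a Table 8 organ limit) and fix it before analysis.
- Keep the number of tests small, state it, and label the section exploratory. Two tests at 5% give at most 1 − 0.95² = 9.75% chance of a false positive if independent.

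The cost is SAP wording and slightly more analysis, with no new data. Estimates stay imprecise at about 7 late events. If a true threshold lies exactly at the chosen cut-off, the continuous comparison has 13-19 points less power than a Chi-square test on that split.

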The addition of chemotherapy to IMRT has been shown to increase acute mucosal damage compared to RT alone, and thus increases the risk of acute toxicity (intensity and duration of mucositis, pain, need and duration of PEG tube...). More importantly, acute toxicity can lead to subacute and late toxicity (so called `consequential late toxicity`)³⁶. It has been reported that bone exposure and osteo- necrosis may result as consequence of overlying mucosal denudation³⁶; more recently it has been postulated that pharyngeal constrictor muscle damage may result from a breakdown of the overlying mucosa, leading to edema, inflammation and ultimately fibrosis of the muscles³⁷.

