1.6 Standard Supportive treatment

Regarding supportive treatment and prophylactic measures to prevent/mitigate toxicity, the following ones are generally pursued as standard of care:

- Dental evaluation and fluoride prescription/administration;
- Speech pathology evaluation including
- Baseline swallowing screening with flexible endoscopic evaluation of swallowing (FEES) followed by a formal modified barium swallowing study (MBSS) if needed. The Penetration/Aspiration Scale (Appendix 4) will be used during modified barium swallow studies.
 - + baseline evaluation of jaw opening, premorbid speech disturbance and dysphonia.
 - + baseline cognitive/language function screening using the Montreal Cognitive Assessment (Appendix 5).
 - + implementation of prophylactic swallowing and trismus prevention exercises prior to initiation of treatment⁴⁶;
 - + education regarding the role of oral hygiene and aspiration pneumonia, products to compensate for xerostomia (e.g., frequent sips of water, oral lubricants, saliva substitutes) and dentrifices.
 - + documentation of the presence of a gastrostomy feeding tube, estimated percent of oral alimentation/hydration via the feeding tube; estimated percentage of PO intake at baseline.
- Nutritional evaluation with pre-treatment correction of weight loss (nutritional impairment is defined as weight loss > 20% in the preceding 3 months or food

intake below 50% of normal requirements in the week preceding enrollment) as needed. A PEG-tube will be placed routinely before or shortly after initiation of IMRT only in those patients who receive chemotherapy in addition to radiotherapy.

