5.3 Target Definition

5.3.1 *Targets* are defined as follows: CTV1 or high dose volume that encompasses the GTV with a margin; in case there is no GTV available (i.e. after tonsillectomy) CTV1 encompasses the tumor bed or where the tumor was before surgery; CTV2, that typically includes the tissue around the gross tumor volume and/or the neck nodal stations that have high (>15%) risk of cancer involvement and/or lymph nodes that look suspicious on imaging; CTV3 includes contralateral lymph nodal stations and lower neck lymph nodal stations which have relatively lower risk (5-15%) of cancer involvement and do not look suspicious at imaging.

5.3.2 Positive lymph nodes are defined as those that meet any of the following criteria on CT: maximum axial diameter > 1cm (>5 mm if retropharyngeal); focal hypoattenuation within the node suggesting necrosis; irregular enhancement pattern; presence of extracapsular penetration as judged by 21peculated margins. Suspicious are those that measure between 7-9 mm in greatest axial dimension in neck levels III through IV; have a rounded appearance defined as a width to length ratio greater than 0.5; lack fatty hilum.

5.3.3 Lymph node stations or levels in the neck follow the surgical nomenclature. A station is considered positive if contains positive lymph nodes. However, in this case, only the positive lymph node(s) and not the whole station is (are) contoured as GTV. Moreover, expansion from GTV to CTV1 does not imply that the whole level will be part of CTV1.

5.3.4 The following (entire) lymph nodal stations are considered at high (>15%) risk of containing microscopic disease when negative/normal on clinical exam and imaging: levels II and III ipsilateral to the site of a positive lymph node in the neck. The entire level is drawn as CTV2⁴².

5.3.5 For lymph node stations different from ipsilateral levels II and III (5.3.5) only the suspicious finding and not the whole level has to be contoured as CTV2;

5.3.6 The following levels are routinely included in CTV3: level IB ipsilateral to neck disease; bilateral levels II, III, IV and V. Controlateral level IB is routinely excluded from any target volume. In the rare case that level IB has a positive or suspicious node, level IB becomes part of the appropriate target volume even in absence of positive level II nodes.

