6 DRUG THERAPY

Chemotherapy will be reserved for patients with T3 lesions (3.1.1) and/or clinically staged nodal disease greater than N1 and/or evidence of microscopic extracapsular extension after neck surgery (T3 and/or N2a \geq 5cm, N2b, N2c, N3 stage cancer or Nx with ECE). Chemotherapy consists of single agent cisplatin or carboplatin.

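### Section 10.3.2 pools both regimens in its dose-by-toxicity tables; if the dose measure differs by regimen, the odds ratio will mix a platinum effect with a dose effect

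*Combined protocol and SAP*

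**What the plan says.** Objective 2.2 is to document side effects over time and to "describe their relationship to pretreatment function and local dose and treated volume". Section 10.3.2 carries it out with two sets of pooled tables.

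- **Toxicity group by dose.** "Patients will be grouped by whether they had none or a grade 0-2 toxicity versus a grade 3+ toxicity". The test is then given as follows: "We will tabulate the frequency of patients in each group by a dichotomous measure of dose and tests for differences with a Chi-square" (with Fisher's test as the alternative).
- **Side-effect count.** The number of side effects is dichotomised, and "frequencies will be compared to dose category and toxicity category using Chi-square or Fisher's exact tests".

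Neither set names a stratum, covariate or model, and no other section supplies one. The organ, metric and cut-off behind the dose measure are not given. Section 10.3.2 also states no significance level.

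Regimen is not randomised. Section 6 says: "Chemotherapy will be reserved for patients with T3 lesions (3.1.1) and/or clinically staged nodal disease greater than N1", or for extracapsular extension after neck surgery. Its parenthesis and the Schema specify N2a of 5 cm or more. All other patients receive IMRT alone.

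**The concern.** Regimen could be tied to both sides of the table.

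- **To dose and volume.** Section 5.3.1 builds the high-dose target around gross tumor. Section 5.3.4 makes whole neck levels part of the 63 Gy volume when they are "levels II and III ipsilateral to the site of a positive lymph node in the neck". Table 6 lets nodal status decide which parts of the lower neck get 50.75 rather than 58.1 Gy. T and N stage, which decide chemotherapy, therefore also influence these volumes.
- **To toxicity.** Section 1.4 states: "The addition of chemotherapy to IMRT has been shown to increase acute mucosal damage compared to RT alone". It adds that acute damage can progress to late damage.
- **To detection.** Table 9, footnote 15, schedules on-treatment blood counts only for chemotherapy patients, and Appendix 1 grades blood-count falls. This can raise their side-effect count for a reason unrelated to radiation dose.

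At stake is how the secondary dose-toxicity result is read. A pooled association could reflect platinum, dose or both, and the planned table could not tell them apart.

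**Working it through.** **1. The plan's own figures.** Section 10.3.2 gives none. In Section 10.1, 60 × 0.85 = 51, against 50 stated. The exact 95% interval for 7/50 (14%) is 5.8–26.7%, which matches the stated 6–27%. These figures are sound but do not bear on this point. They do fix the scale: 15% of 50 is 7.5, so about 7 late events are expected at the target.

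**2. Assumptions.** The documents give no regimen mix, no toxicity rate by regimen and no dose cut-off. I assumed:

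- n = 50 and chemotherapy share c = 0.60;
- high-dose share hC = 70–80% with chemotherapy and hR = 20–30% without;
- toxicity tC with chemotherapy and tR without, and no dose effect within either regimen;
- a two-sided level of 0.05.

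**3. Formulas.**

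- Share in the high-dose category: pH = c·hC + (1−c)·hR
- Toxicity at high dose: [c·hC·tC + (1−c)·hR·tR] / pH
- Toxicity at low dose: [c·(1−hC)·tC + (1−c)·(1−hR)·tR] / (1−pH)

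**4. Upper end near the target** (tC 20%, tR 5%, hC 80%, hR 20%; overall toxicity 14%).

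- pH = 0.48 + 0.08 = 0.56
- High dose: (0.096 + 0.004)/0.56 = 17.9%
- Low dose: (0.024 + 0.016)/0.44 = 9.1%
- Odds ratio: (0.179/0.821)/(0.091/0.909) = 2.17, where the truth is 1.0

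**5. Lower end near the target** (tC 18%, tR 10%, hC 70%, hR 30%; overall 14.8%).

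- pH = 0.42 + 0.12 = 0.54
- High dose: (0.0756 + 0.012)/0.54 = 16.2%
- Low dose: (0.0324 + 0.028)/0.46 = 13.1%
- Odds ratio: 1.28

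**6. False-positive rates.** Each scenario was simulated 20,000 times. Ranges cover the four combinations of hC 70% or 80% with hR 20% or 30%. The stratified test is the large-sample Cochran-Mantel-Haenszel (CMH) test.

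| Toxicity, chemo / alone | Overall | Spurious OR | Chi-square | Fisher | CMH by regimen |
|---|---|---|---|---|---|
| 18% / 10% | 14.8% | 1.3–1.5 | 5–7% | 3–4% | 4–5% |
| 20% / 7% | 14.8% | 1.5–1.9 | 7–10% | 4–6% | 5% |
| 20% / 5% | 14.0% | 1.6–2.2 | 8–12% | 5–7% | 4–5% |
| 30% / 10% | 22% | 1.6–2.0 | 9–16% | 6–11% | 5% |
| 50% / 20% | 38% | 1.6–2.1 | 14–25% | 10–20% | 5% |

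Overall toxicity is 0.6·tC + 0.4·tR; for the last row, 0.30 + 0.08 = 38%.

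**7. Control.** With hC = hR = 50%, the odds ratio is 1.0 and Chi-square rejects in about 5% of trials. The distortion exists only if dose category and regimen are associated.

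**The case against.** The strongest reply is that the tie between regimen and dose is looser than it looks. Four points support it.

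- Both regimens use the same four prescription levels (Section 5.6, Table 6).
- Section 1.2 reports that, up to T3, staging by dimension did not correlate with tumor volume in two studies. It quotes 0–32.5 cm³ for T2 and 0–48 cm³ for T3.
- Table 7 sets the same organ limits for every patient, and Section 5.6.4 ranks that group above target coverage.
- The rule in Section 5.3.4 applies to any positive node. It therefore also covers N1 and smaller N2a patients treated with IMRT alone.

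All of this stands. A reader might infer that tumor extent fixes dose, so that confounding is certain. The documents support only an influence on volumes, and the undefined dose measure leaves its strength open.

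A reader might also infer that the tube policy ("A PEG-tube will be placed routinely before or shortly after initiation of IMRT only in those patients who receive chemotherapy in addition to radiotherapy") makes chemotherapy patients grade 3 cases. It does not do so by itself: Appendix 1 records the tube separately as yes or no, and its grade 3 rows mostly require tube feeding to be indicated for severe dysfunction.

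On size, Fisher's test is one of the two planned tests and the natural one with about 7 events. Near the target it stays at 3–7%. The 38% scenario is out of line with the design for late toxicity: 38% of 40 is about 15, the stopping count in Section 10.1. It is relevant only to the acute phase, which Objective 2.2 also covers.

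These points reduce the false-positive rate. They do not remove the bias in the odds ratio or give a reason to pool.

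**Conclusion.** The point holds in a limited form. The planned tables are pooled and unadjusted, regimen follows tumor and node extent, and the protocol itself links chemotherapy to toxicity. If the chosen dose measure differs by regimen, the crude odds ratio is biased. If it does not, there is no bias from this source.

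The actual size cannot be derived from the documents. Under the stated assumptions and near the 15% target, the spurious odds ratio is about 1.3–2.2. False positives run from nominal (5–6%) to about 12% with Chi-square and 3–7% with Fisher. At acute-phase rates they reach about 24–25% and 20%. Stratification returns them to about 5%.

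Two wider conclusions might be drawn, and neither is supported. The primary endpoints are not compromised, because they are single-arm proportions that use no dose comparison. Nor would wrong organ dose limits follow: no section says limits will be derived from this trial, and the objective is secondary and descriptive. I would class this as a cheap improvement.

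**What to change.** In Section 10.3.2:

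1. Name the dose (or volume) measure and its cut-off in advance.
2. Show every dose- or volume-by-toxicity table, and the side-effect-count table, separately for IMRT alone and IMRT plus platinum.
3. Replace the pooled test with an exact Cochran-Mantel-Haenszel test stratified by regimen, and report a common odds ratio with its 95% CI.
4. Label the result exploratory.

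This takes a sentence or two of text. Regimen is known for every patient, so no new data, visits or patients are needed. The price is a somewhat wider interval, and with about 7 late events power is low. Stratifying by regimen does not remove confounding by tumor extent within a regimen, and the report should say so.
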